## 10. STUDY ASSESSMENTS

## **10.1.** Screening Assessments

The results of the screening assessments should be reviewed to ensure that the patient continues to satisfy all entry criteria and otherwise remains a satisfactory patient for the extension study. Laboratory assessments obtained at the final visit of the double-blind lead-in HONOR study or the 12-week open-label extension study P303 will not be available prior to the patient's entry into the extension study, but should be reviewed within 7 days when they become available, to ensure the patient's ongoing well-being.

## 10.2. Efficacy Assessments

A secondary objective of this study is to evaluate the long-term effect of TNX-102 SL and these endpoints are derived from both clinician-administered and subjective patient-completed assessments. The clinician-administered assessments must be administered by qualified and trained individuals at each clinical site. Study specific training will be required before new staff that were not trained for the lead-in study are allowed to administer these scales. In an attempt to minimize variability in responses of a given patient over time, it is important that the same rater administer the scales to a given patient throughout the study as much as possible. It is also important that the assessments, including those that are patient-completed, be conducted in the specified order, according to specific instructions, and in a setting where the patient has minimal distractions and sufficient time to complete them. After completion of these assessments, the study coordinator should review the responses for completeness with the patient.

## 10.2.1. Clinical Global Impression of Improvement (CGI-I)

The CGI-I is a commonly used clinician-rated scale designed to assess overall clinical improvement (change) since baseline. The CGI-I will be completed at each in-clinic visit after baseline. It will be the responsibility of the Principal Investigator or his qualified designee to assess change in the subject's overall status.

## 10.2.2. Sheehan Disability Scale (SDS)

The SDS scale is a self-report questionnaire that was designed to assess the subject's view of the degree to which symptoms have disrupted work, social life/ leisure activities, and family life/ home responsibilities during the past week. In addition, the SDS asks the subject to provide the number of days or work lost as well as unproductive days. The SDS will be administered at each in-clinic visit.

## 10.2.3. PROMIS Sleep Disturbance Scale

PROMIS refers to the Patient-Reported Outcome Measurement Information System (www.nihpromis.org), an NIH-funded initiative to develop instruments to be used across chronic conditions. The PROMIS scale for sleep disturbance (form 8a) will be administered at all inclinic visits.

## 10.2.4. Beck Depression Index (BDI-II)

BDI-II refers to the patient-rated assessments of depressive symptomology. The BDI-II will be administered at all in-clinic visits. Each patient's response to the BDI suicidality question (item 9) should be reviewed and compared to the C-SSRS responses to ensure careful assessment of any suicidal ideation and resolution of any discrepancies between the self-reported BDI-II and the C-SSRS interview.

## 10.2.5. PTSD Checklist-Specific Version (PCL-S)

Developed by the National Center for Posttraumatic Stress Disorder, the PCL-S is a 17-item self-report measure reflecting DSM-IV symptoms of PTSD. The PCL-S aims to link symptom endorsements to a specified event or stressful experience, which for P306 has been identified by the subject as their Index Trauma during the lead-in double blind study (TNX-CY-P301). Respondents rate each item from 1 ("not at all") to 5 ("extremely") to indicate the degree to which they have been bothered by that particular symptom over the past month.

In addition, the long-term safety of TNX-102 SL on PTSD based on PCL-S completed by patients in Visit 5 (Week 28) and Visit 6 (Week 40) and Visit 7 (Week 52 for patients enrolled under Track B), is assessed with this scale. The mean change in PCL-S total score and PCL-S clusters scores from Visit 5 (Week 28) to Visit 6 (Week 40), or to Visit 7 for Track B patients will detect any potential worsening in total PTSD score or symptoms clusters in the final 12-weeks, or 24-weeks for Track B patients, of the study. Since PCL-S is added to the study when a significant number of patients have passed the Visit 4 (Week 16 time point, Visit 5 (Week 28) is chosen as the "baseline" for PCL-S in order to capture the vast majority of the patients who enrolled in the study from its beginning.

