# 12.2. Evaluation of Efficacy

As this is a long-term safety study, minimal conclusions will be available concerning long-term efficacy. The efficacy analyses will focus on durability of the response achieved prior to entry into this extension study, based on the CGI-I for patients in Track A and for patients on active drug in the lead-in HONOR study or the P303-early-terminated patients (due to IA results) who were on placebo in P301 in Track B. In addition, durability of response for both Track A and B patients will be assessed by measuring the change in PCL-S scores from Visit 5 (Week 28) to Visit 6 (Week 40) in order to detect any potential worsening in PTSD symptoms as a result of longer term use of TNX-102 SL 5.6 mg. For Track B patients, an additional Visit 7 (Week 52) PCL-S assessment with be available for subset analysis of durability of response.

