h Visit 5(Week 28) will be the "baseline" for PCL-S because it will capture the vast majority of the patients who have enrolled from the start of P306. The mean change in PCL-S total score and PCL-S clusters scores from Visit 5 (Week 28) to Visit 6 (Week 40), and to Visit 7 for Track B patients, will detect any potential worsening in total PTSD score or symptoms clusters due to long-term treatment of TNX-102 SL in the final 12-weeks, and 24-weeks for Track B patients, of the study.

<sup>i Track A patients only.

<sup>j Track B patients only.

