2.2 Study Endpoints

2.2.1 Efficacy Endpoints

Comparisons will be made at each study week of data collection to the baseline of this study.

Efficacy endpoints include:

- Average CGI-I score (scored 1-7)
- Proportion of patients with a CGI-I score of "very much improved" or "much improved"
- Change from baseline in the SDS total score
- Change from baseline in the individual items assessed using the SDS
- Change from baseline in patients' quality of sleep using the PROMIS Sleep Disturbance scale
- Change from baseline in BDI-II score
- Change from week 28 to week 40 in PCL-S
- Change from week 28 to week 52 in PCL-S (Track B subjects only)
- Change from week 40 to week 52 in PCL-S (Track B subjects only)

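### The mean PCL-S change describes average drift and cannot by itself detect any worsening; no planned output says how many patients worsened or by how much

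*Protocol*

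**What the plan says.** Protocol 10.2.5 states that "the PCL-S is a 17-item self-report measure", with each item rated 1 to 5. Its sentence on the analysis begins "The mean change in PCL-S total score and PCL-S clusters scores from Visit 5 (Week 28) to Visit 6 (Week 40"), extends to Visit 7 for Track B, and says that this mean change "will detect any potential worsening in total PTSD score" or in its symptom clusters. Appendix 1 footnote h repeats the claim and adds a cause: the mean change "will detect any potential worsening in total PTSD score or symptoms clusters due to long-term treatment of TNX-102 SL".

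Two other places are related but do not tie detection to the mean. Protocol 12.2 says that the change in PCL-S scores is measured "in order to detect any potential worsening in PTSD symptoms as a result of longer term use of TNX-102 SL 5.6 mg". SAP 2.2.1 lists "Change from week 28 to week 40 in PCL-S" and two further intervals for Track B as efficacy endpoints, and says nothing about detection. Protocol 6.3.1 also names the PCL-S change as a safety endpoint.

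The protocol synopsis plans n, mean, SD, median, minimum and maximum for the PCL-S, and SAP 7.1 plans the same for continuous variables in general. Protocol 12.1 promises listings by patient. Neither document defines a PCL-S change that counts as worsening, plans a count of patients who worsened on the scale, or plans a display of the distribution of individual changes.

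**The concern.** The question behind the endpoint is whether patients deteriorate late in long-term treatment. That is a question about individuals, and a mean answers a different one: whether the group drifts on average. If a minority deteriorates while the rest edge upward, the mean can sit at zero or show a slight improvement.

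Offsetting gains are plausible here. Protocol 6.1 allows currently approved PTSD therapies, and Protocol 8.5 relaxes the lead-in restrictions on other medication and on trauma-focused psychotherapy.

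The PCL-S is the only PTSD-specific symptom scale collected in this study, and it serves both a safety endpoint and the durability question. For laboratory values, vital signs and the C-SSRS, the SAP plans shift tables or patient counts (SAP 10.2, 10.3, 12.3, 12.4). The PCL-S has no equivalent. The only categorical efficacy analysis, in SAP 9.1.2, counts patients improved on the CGI-I, not patients who are worse.

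**Working it through.** The documents state no SD, power, cut-off or detectable change for the PCL-S, so there is no figure of the plan's own to reproduce.

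**Inputs.** From Protocol 10.2.5: 17 items scored 1 to 5, so the total runs from 17 x 1 = 17 to 17 x 5 = 85, and a rise is a worsening. From Protocol 6.2: up to 200 patients. From the synopsis: at least 50 with 52 weeks of exposure. Assumed: share worsening w = 5-20%, size of worsening d = 10-20 points, SD of individual change 8-12, paired n = 50-200.

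**Step 1: cancellation (needs neither n nor SD).** If a share w worsens by d and the rest improve by g, the mean change is w x d - (1 - w) x g. It is zero when g = w x d / (1 - w). The cancelling gain g, in points, is:

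| Share worsening | d = 10 | d = 15 | d = 20 |
|---|---|---|---|
| 5% | 0.53 | 0.79 | 1.05 |
| 10% | 1.11 | 1.67 | 2.22 |
| 20% | 2.50 | 3.75 | 5.00 |

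For the middle cell, 0.10 x 15 / 0.90 = 1.67 points, or 1.67 / 17 = about 0.1 point per item. With a gain of 2 points instead, the mean is 0.10 x 15 - 0.90 x 2 = -0.3, an apparent improvement.

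**Step 2: the mean with its sampling error.** The plan attaches no test to the PCL-S, so a 95% CI is used only as a yardstick. The total SD is sqrt(SD^2 + w(1 - w)(d + g)^2), and the chance that the lower limit exceeds zero is about Phi(mean / SE - 1.96). With w = 10%, d = 15 and SD = 10:
- g = 1.67: the mean is 0 and the chance is 2.5% at any n.
- g = 1: the mean is 1.5 - 0.9 = 0.6, and the chance is 6%, 8% and 12% at n = 50, 100 and 200.
- g = 0: the mean is 1.5, and the chance is 16%, 28% and 49%. Over SD 8-12 it is 13-21% at n = 50 and 38-64% at n = 200.

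**Step 3: would the other planned statistics show it?** Take w = 10%, d = 15, g = 1.67 and SD = 10 in both groups.
- SD: it rises from 10 to sqrt(100 + 0.09 x 16.67^2) = 11.2.
- Median: it is about -0.44, since 0.9 x Phi(0.123) + 0.1 x Phi(-1.544) = 0.50. That is less than half a point from the mean of 0.
- Maximum: the largest of 90 normal values averages about 2.47 SD above their mean, so the patients who did not deteriorate would by themselves give about -1.67 + 24.7 = 23. A change of 15 points would not stand out.

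**Step 4: what a count adds, and its limit.** A count does not cancel. For 10 of 100 patients the exact 95% CI is 4.9-17.6%. But with no true change and an SD of 10 (8-12), 1 - Phi(5/SD) = 31% (27-34%) would rise by 5 points or more, and 1 - Phi(10/SD) = 16% (11-20%) by 10 or more. In the Step 3 example, 0.9 x (1 - Phi(1.167)) + 0.1 x (1 - Phi(-0.5)) = 18% rise by 10 or more, close to the 16% from fluctuation alone. A one-sided count at a low cut-off is therefore easily misread. The falls and the whole distribution must stand beside it.

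**The case against.** The strongest case on the other side is that this is loose wording and not a defect of analysis. The object of the sentence is worsening in the total or cluster scores, which can be read as group drift. The mean is not reported alone. The listings show every patient's values. Protocol 10.4.1 has PTSD symptoms reported as adverse events when they significantly worsen and fall outside the patient's normal experience, and SAP 10.1 counts adverse events by patient. The CGI-I has three grades for worse. Protocol 12.2 itself expects only minimal conclusions on long-term efficacy.

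Much of this stands, and it rules out three stronger readings.
- A reader might infer that late deterioration would be invisible in the outputs. It would not: the spread, the extremes, the listings and the adverse events all carry some of it.
- A reader might infer that a mean near zero will be reported as no worsening. No rule in the documents says so, and no margin or test is attached to the PCL-S.
- A reader might take Protocol 12.2 and SAP 2.2.1 as further statements that the mean detects worsening. Neither names the mean.

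What does not stand is that these outputs fill the gap. Step 3 shows that the SD, median and maximum can look unremarkable. A listing without a summary gives no rate. The adverse event route depends on the patient's opinion and not on the scale. The CGI-I compares with the P306 baseline, not with Week 28, and only improvement is tabulated as a category.

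The objection that worsening counts in a single-arm study pick up ordinary fluctuation is also correct, and it shapes the fix.

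**Conclusion.** The concern holds in a limited form. Protocol 10.2.5 and Appendix 1 footnote h credit the mean PCL-S change with a property that it lacks, and no planned output states how many patients worsened on the scale or by how much. The cancellation result is arithmetic and needs no SD or sample size. Its size, a gain of 1.67 points offsetting a 15-point loss in 10% of patients (0.5-5.0 points over the range examined), rests on assumed shares and sizes. The chances in Step 2 also rest on an assumed SD of 8-12, 50-200 paired patients and a normal approximation.

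Footnote h goes further by attributing worsening to long-term treatment. A single-arm change, whether a mean or a count, cannot support that attribution. No other analysis is invalidated; the gap is one of description and wording.

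**What to change.** Keep the mean change and its descriptive statistics. In the SAP, add:
- A cumulative distribution plot of individual PCL-S changes, Week 28 to Week 40 for all patients and Week 28 to Week 52 for Track B.
- The number and percentage of patients, with exact 95% CIs, whose total rises and, symmetrically, falls by at least cut-offs that the sponsor fixes and justifies before the outputs are run. If outputs already exist, label the table post hoc, as SAP section 1 provides.
- The denominator, meaning patients with both scores. The early termination procedures in Protocol 9.6 do not include the PCL-S, so patients who leave after Week 28 without another score contribute no change.
- A statement that without a control arm these counts cannot separate natural fluctuation from deterioration on drug.

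In the protocol or the study report, replace the detection claim with wording that the mean describes average change, and that the distribution and counts describe individual deterioration. The protocol estimated completion in September 2019 and the SAP cites a 2023 source, so the SAP and the report are the practical places.

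The cost is one small table, one figure and a few sentences, from data already collected. The downsides are that the cut-off is a judgement, which the plot partly offsets, and that some counted rises will be ordinary fluctuation.

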## 10.3. Pharmacogenomics Testing

For pharmacogenomic analysis, a single blood draw collected in two PAXgene DNA tubes will be obtained from each patient after they have provided separate written, signed informed consent for pharmacogenomic analysis. The purpose of this testing is to allow exome sequencing and analysis for genetic variants related to treatment response to TNX-102 SL. It is presumed that unused sample will be stored up to fifteen years, and potentially utilized to develop a pharmacogenomic test for determining likelihood of treatment response to TNX-102 SL. A decision not to participate in optional pharmacogenomic testing will not affect the patient's eligibility for the main study. Patients have the right to stop participating at any time during the study or during the time of sample storage, and, if a patient decides to withdraw from the pharmacogenomics portion of this study, any remaining sample will be destroyed and not used for further research. Data collected before a patient's withdrawal from the pharmacogenomics portion of this study will remain in the research database.

## 10.4. Safety Parameters

Safety will be assessed by evaluation of adverse events, responses on the C-SSRS, clinical laboratory tests, examinations of the oral cavity, vital signs, weight, patient-rated assessments of depressive symptomology (BDI-II) and PTSD symptomology (PCL-S).

#### 10.4.1. Adverse Events (AEs)

Patients will be monitored for AEs throughout the study, from the time the patient signs an informed consent onward. AEs that are spontaneously reported, elicited or observed are to be recorded on the CRF with the date, time of onset, date and time of resolution, severity, seriousness, causality (relationship to study medication), actions required, and outcome.

To elicit AEs, non-leading, simple questions with minimal connotations should be used as the initial questions at all evaluation points during the study. Examples of these questions can be:

- How have you felt since your last visit?
- Have you had any health problems since your last visit?

If an AE occurs, the investigator will institute support and/or treatment as deemed appropriate. If a non-serious AE is unresolved on the last day of the study, an effort should be made to follow up until the AE is resolved or stabilized, the patient is lost to follow-up, or there is some other resolution of the event

There are many symptoms associated with PTSD that can vary in intensity and frequency over time. Only symptoms that significantly worsen or become more frequent, and in the opinion of the patient are outside of their normal experience, should be reported as adverse events.

If a patient reports an oral adverse event other than numbness, tingling or bitter taste, the Investigator should examine the oral cavity to confirm presence or absence of any lesion or other abnormality, and document the exam. Additional details related to onset, duration, severity and reversibility of the oral event will also be documented.

## 10.4.1.1. Columbia-Suicide Severity Rating Scale (C-SSRS)

The C-SSRS is a clinician-administered interview developed by researchers at Columbia University to assess suicide risk and to track suicidal ideation and behavior during clinical trials. This scale is intended to be administered by individuals who have received training in its administration. The questions contained in the Columbia-Suicide Severity Rating Scale are suggested probes. Ultimately, the determination of the presence of suicidal ideation or behavior depends on the judgment of the individual administering the scale.

The "since last visit" version of the C-SSRS will be completed at all study visits. Note that if there has been a significant change in responses to this scale indicative of increased suicide risk, appropriate intervention should be prescribed Section 10.4.1.2 and an AE should be recorded. The patient's response to BDI-II item 9 (suicidal ideation) should be reviewed prior to conducting the C-SSRS at the in-clinic visits to ensure the patient's responses are consistent between the BDI and the C-SSRS (and/or the reason for any inconsistency documented in the patient's chart).

## 10.4.1.2. Safety Planning Intervention (SPI)

The C-SSRS is completed at every visit in order to assess for changes in suicidality during the study. If a patient scores a 4 or 5 on the Suicidal Ideation section of the C-SSRS at a clinic visit following enrollment, the patient should be withdrawn from the study and referred for appropriate emergency care. A score of 4 or 5 should also result in the reporting of a SAE.

If a patient scores a 2 or 3 on the Suicidal Ideation section of the C-SSRS at any visit, the investigator should consider the implementation of a Safety Planning Intervention (SPI). The recommended SPI for this study is the plan developed by [name] and [name] which has been adopted by the US Veteran's Administration (VA) (Stanley & Brown, 2012). The VA SPI is a brief clinical intervention aimed at mitigating suicide risk. It consists of a written, prioritized list of coping strategies and sources of support that patients can use to alleviate a suicidal crisis. Sites may use an internally-developed SPI if similar in scope and purpose to the VA SPI.

#### 10.4.1.3. Visual Examination of Oral Cavity

A visual examination of the oral cavity should be done at Baseline/Visit 1 (or the Week 12 Visit of the 12-week open label study) and after 28 weeks (Visit 5) and 40 weeks (Visit 6) for Track A patients, or after 52 weeks of treatment (Visit 7) for Track B patients, and/or at ET. In addition to these regularly scheduled examinations, a visual inspection of the oral cavity (including the sublingual area) should be done any time a patient reports a lesion or other finding in the oral cavity other than numbness, tingling or bitter taste, in order to document the presence or absence of any visible abnormalities. Additional details related to onset, duration, severity and reversibility of oral events will also be documented in the CRF.

## **10.4.1.4.** Vital Signs

Vital signs (sitting blood pressure and heart rate, respiratory rate, oral temperature, and weight) will be assessed at Visits 1, 3, 4, 5, 6 and 7 (Visit 7 for Track B patients only). Height will be transferred from the lead-in study database for BMI calculations (done at Baseline and Visit 6 for Track A patients or Visit 7 for Track B patients).

## 10.4.1.5. Clinical Laboratory Assessments

The clinical laboratory evaluations to be performed in this study are listed in Table 2. All tests will be performed at Baseline/Visit 1 (or the Week 12 Visit of the 12-week open label HONOR study), after 28 weeks (Visit 5) and after 40 weeks of treatment (Visit 6) for Track A patients, or after 52 weeks of treatment (Visit 7) for Track B patients, or ET.

With the exception of the urine pregnancy tests, all clinical laboratory evaluations will be analyzed via a central clinical laboratory, and information regarding appropriate sample volume, collection tubes, sample labeling and handling, and shipment will be provided in a study manual. Each clinically significant abnormal laboratory value or other clinically meaningful abnormality should be followed until the abnormality resolves or until a decision is made that it is not likely to resolve. If such abnormalities do not return to normal within a reasonable period, their etiology should be identified and Tonix or designee should be notified. Treatment-emergent clinically significant abnormalities in laboratory values will be recorded as AEs.

**Table 2:** Clinical Laboratory Assessments

Clinical chemistry	Hematology
Alanine aminotransferase (ALT)	Hematocrit

Alkaline phosphatase	Hemoglobin
Aspartate aminotransferase (AST)	MCH concentration (MCHC)
Bilirubin (total)	Mean corpuscular hemoglobin (MCH)
Blood urea nitrogen (BUN)	Mean corpuscular volume (MCV)
Calcium	Platelet count
Chloride	Red blood cell (RBC) count
Cholesterol (total)	White blood cell (WBC) count differential
Creatinine kinase (CK)	Neutrophil count (absolute and %)
Creatinine	Lymphocyte count (absolute and %)
Glucose	Monocyte count (absolute and %)
Phosphorus	Eosinophil count (absolute and %)
Potassium	Basophil count (absolute and %)
Protein (albumin and total)	WBC count
Sodium	
Urine Pregnancy Test (qualitative dipstick) a	
Pharmacogenomic testing (optional; can be obtained at any visit, including an early termination visit)	

<sup>a Pregnancy testing for females of child-bearing potential only. A positive pregnancy test mandates withdrawal from the study (all visits).

